5.2. Study Population

Patients who were California or Louisiana residents in the HealthVerity claims database will be defined using the following hierarchical definition:

- Persons who have their enrollment file record indicating a patient location of California or Louisiana in HealthVerity claims enrollment file.
- 2. Persons who have a patient state location other than California or Louisiana in HealthVerity claims enrollment but have one or more records in the California or Louisiana Immunization Registry. Examples include people who previously lived in Texas but moved to California and received a vaccine, or persons who crossed state lines for a vaccine and remain in their non-California state in claims data.

Patients who meet the following criteria will be included in the analysis:

5.2.1. Inclusion Criteria

- Born in 2006-2023 (as age 0-17 years in 2023, owing to the data providing year but not month or day of birth).
- At least six months of pharmacy and medical enrollment in HealthVerity prior to index date (FDA EUA date per age group vaccine). Six months was selected to allow for analysis to include children age <1yr. A gap of up to 30 days will be allowed.
- Have been a State of California/Louisiana resident for at least six months prior to index date (FDA EUA date per age group and vaccine). A gap of up to 30 days will be allowed.

5.2.2. Exclusion Criteria

- Currently pregnant (with a code list for current pregnancy and 9 months lookback) or immunocompromised (as per McGrath, Malhotra, Miles et al 2023) at the time of study index (definitions are provided in the Protocol Annex)
- 2. Individuals with discrepancies in sex and/or year of birth between HealthVerity claims and California/Louisiana immunization registry datasets, or missing sex in both datasets. In cases where sex or year of birth is unknown in either the claims or registry by available in the other, individuals will be included and the information from the dataset where year of birth or sex is available will be used, regardless of whether the information stemmed from claims or registry data.
- Persons with a diagnosis of COVID-19 in any setting ≤ 90 days prior to index (FDA EUA date per vaccine)
- Receipt COVID-19 vaccine ≤ 90 days prior to index (FDA EUA date per vaccine).
- Persons who died before index date, operationalized as the last day in the month and year of death.

5.2.3. Subgroups and Stratification

Results will be stratified by age group (overall, age 6 months – 4 years, 5-11, 12-17).

Additionally, the analysis of the primary outcome will be stratified by state of residence. As tests and measures of heterogeneity can be affected by large sample sizes, clinical relevance will be used to assess the difference in VE estimates between the two registries. If a difference is deemed clinically relevant, secondary and exploratory outcomes may be additionally stratified by state of residence.

The following subgroups will be used to evaluate VE for the XBB.1.5 vaccine:

- Receipt of BA.4/5 bivalent vaccine
- Receipt of two prior doses of mRNA COVID-19 vaccine and no prior receipt of BA.4/5 bivalent vaccine
- No prior receipt of a COVID-19 vaccine

Of note, persons who received 1 mRNA wildtype dose, or received 2 wildtype doses <21 days apart, do not meet any of these criteria and will be included in the main analysis (which does not consider prior vaccination history) but excluded in these subgroup analyses of vaccination history.

5.3. Variables

5.3.1. Exposures

The exposure of interest is the BNT162b2 XBB.1.5 mRNA vaccine.

Information on vaccination status will continue to be collected on or after the authorization/approval date, therefore vaccination status will be considered as a time-varying exposure. Patients will be assigned as vaccinated or unvaccinated according to their vaccination status by each person-time record during the follow-up. A patient will be considered vaccinated from 14 days after their BNT162b2 vaccination date till the remainder of their follow-up.

The source of the exposure variables are the California and Louisiana vaccine registries and the HV (HealthVerity) Claims database. Clinical Vaccines Administered code (CVX), National Drug Codes (NDC) and Current Procedural Terminology® (CPT) codes used to identify the XBB.1.5 and BA.4/5 vaccinations are listed in the Protocol Annex.

XBB vaccinations will be enumerated using the following hierarchical definition:

- Any person in HealthVerity claims data who has a record in the California/Louisiana Immunization Registry with a CVX code indicating having received the BNT162b2 XBB.1.5 monovalent mRNA vaccine will be considered vaccinated 14 days after registry event date.
- 2. Any person in HealthVerity claims data who has a record in the California/Louisiana Immunization Registry that does not include a CVX code but lists the vaccine manufacturer as Pfizer with a vaccination date on or after 09/11/2023 indicating having received the BNT162b2 XBB.1.5 monovalent mRNA vaccine will be considered vaccinated 14 days after registry event date.

- Any person in HealthVerity claims data who has a record in the California/Louisiana Immunization with an event indicating having received the BNT162b2 XBB.1.5 monovalent mRNA vaccine will be considered vaccinated 14 days after registry event date.
- 4. Any person in HealthVerity claims data who does not have a record in the California/Louisiana Immunization Registry but has a pharmacy claim with an NDC code indicating a BNT162b2 XBB.1.5 monovalent mRNA vaccine dose will be considered vaccinated 14 days after claim date.
- 5. Any person in HealthVerity claims data who does not have a record in the California/Louisiana Immunization Registry and does not have a pharmacy claim with an NDC code indicating a BNT162b2 XBB.1.5 monovalent mRNA vaccine dose but has a medical claim with a CPT code indicating a BNT162b2 XBB.1.5 monovalent mRNA vaccine dose will be considered vaccinated 14 days after claim date.
- 6. Any person in HealthVerity claims data who does not have a record in the California/Louisiana Immunization Registry, does not have a pharmacy claim with an NDC code indicating a BNT162b2 XBB.1.5 monovalent mRNA vaccine dose and does not have a medical claim with a CPT code indicating a BNT162b2 XBB.1.5 monovalent mRNA vaccine dose will be considered BNT162b2 XBB.1.5 unvaccinated.

BA. 4/5 vaccinations will be enumerated in the same manner as XBB. 1.5.

5.3.2. Outcomes

The outcomes of interest are presented in Table 5.2.

Table 5.2 Outcomes Variables

Outcome Type	Variable	Data source(s)	Operational definition	
Primary outcome	COVID-19 diagnosis	HV Claims	Any encounter regardless of diagnosis setting with ICD-10-CM code: U07.1.	
Secondary outcomes	COVID-19 outpatient encounter	HV Claims	Outpatient encounter with ICD-10-CM code: U07.1	
	COVID-19 hospitalization	HV Claims	Hospitalizations "for COVID-19" were defined as those with an inpatient encounter at an acute care facility with ICD-10-CM code: U07.1 "COVID-19" that did not have an additional incidental code (for unintentional injury, physical trauma, poisoning, short-stay (<2 days) childbirth or severe and persistent mental illness) or a U07.1 hospitalization where treatment used solely for COVID-19 (eg, remdesivir) was identified regardless of accompanying diagnoses.	
			As a sensitivity analysis, we will relax this definition to consider any hospitalization with a U07.1 code, without consideration of incidental findings.	
	COVID-19 emergency department visit	HV Claims	Emergency department visit with ICD-10- CM code: U07.1	
	COVID-19 critical illness	HV Claims	Intensive care unit [ICU] admission, mechanical ventilation, or inpatient death. If sample size allows (Section 5.5), we will evaluate VE against each component separately	

Outcome Type	Variable	Data source(s)	Operational definition
	Non-COVID- 19 respiratory infections (pneumonia, respiratory syncytial virus (RSV), rhinovirus, antibiotic prescriptions)	HV Claims	Any encounter regardless of setting with ICD-10-CM code for diagnosis or NDC codes for antibiotics (codes in the Protocol Annex). If sample size allows (Section 5.5), we will evaluate VE against each component separately
	Negative control outcome, such as accidental injury, ingrown toenail or atopic dermatitis	HV Claims	Any encounter regardless of setting, with ICD-10-CM code for negative control outcomes (codes in the Protocol Annex)
Exploratory outcomes	COVID-19 urgent care encounter	HV Claims	An urgent care encounter with ICD-10-CM code: U07.1 "COVID-19"
	All-cause mortality after COVID-19 encounter	HV Claims and HV Mortality Database	HealthVerity ID in Mortality Database within 3-months of COVID-19 encounter, regardless of setting
	All-cause mortality after COVID-19 outpatient encounter	HV Claims and HV Mortality Database	HealthVerity ID in Mortality Database within 3-months of COVID-19 outpatient encounter
	All-cause mortality after COVID-19 inpatient encounter	HV Claims and HV Mortality Database	HealthVerity ID in Mortality Database within 3-months of COVID-19 inpatient encounter

Outcome Type	Variable	Data source(s)	Operational definition	
	All-cause mortality after COVID-19 emergency department encounter	HV Claims and HV Mortality Database	HealthVerity ID in Mortality Database within 3-months of COVID-19 emergence department encounter	
	All-cause mortality after COVID-19 critical illness	HV Claims and HV Mortality Database	HealthVerity ID in Mortality Database within 3-months of COVID-19 critical illness	
	All-cause mortality after COVID-19 urgent care encounter	HV Claims and HV Mortality Database	HealthVerity ID in Mortality Database within 3-months of COVID-19 urgent care encounter	

Each outcome will be assessed independently and experiencing one outcome will not be a censoring event for another outcome. Where a patient has multiple instances of the same outcome, the first one will be used.

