8.3. Variables

TABLE 3. EXPOSURE VARIABLES

Variable	Data source(s)	Operational definition
BNT162b2 XBB.1.5 mRNA vaccine after FDA authorization date and 14 or more days	California/Louisiana Immunization Registry as well as HV Claims	Vaccines will be enumerated as per section 8.2. Date of vaccination will be used to assess time-based inclusion/exclusion criteria.
BNT162b2 BA.4/5 mRNA vaccine after FDA authorization date and 14 or more days	California/Louisiana Immunization Registry as well as HV Claims	Vaccines will be enumerated as per section 8.2. Date of vaccination will be used to assess time-based inclusion/exclusion criteria.
Influenza vaccine	HV Claims	Identified using NDC or CPT code

TABLE 4. OUTCOME VARIABLES

Variable	Data source(s)	Operational definition
COVID-19 diagnosis	HV Claims	Any encounter regardless of diagnosis position or setting with ICD-10-CM code: U07.1
COVID-19 hospitalization	HV Claims	Inpatient encounter at an acute care facility with ICD-10-CM code: U07.1 "COVID-19" listed in any diagnosis position
COVID-19 emergency department visit	HV Claims	Emergency department visit with ICD-10-CM code: U07.1

Variable	Data source(s)	Operational definition
COVID-19 outpatient encounter	HV Claims	Outpatient encounter with ICD-10-CM code: U07.1
COVID-19 critical illness	HV Claims	Intensive care unit [ICU] admission, mechanical ventilation, or inpatient death
All-cause mortality	HV Mortality Database	HealthVerity ID in Mortality Database
Non-COVID-19 respiratory infections (pneumonia, RSV, rhinovirus, antibiotic prescriptions)	HV Claims	Any encounter regardless of setting with ICD-10- CM code for diagnosis or NDC codes for antibiotics (Codes in Annex)
Hospitalization length of stay (days)	HV Claims	Date of service end – date of service
ICU admission	HV Claims	As per HealthVerity's suggestion, ICU related services/inpatient stays will be found on Institutional claims, and can be identified using revenue codes (codes in Annex).
Invasive ventilation	HV Claims	CPT, HCPCS and ICD-10 (codes in Annex)
Cost of hospitalization	HV Claims	Using HealthVerity's "Proxy Financial Algorithm", based on CMS Medicare prospective payment system fee schedules
Influenza diagnosis	HV Claims	Any encounter regardless of setting with ICD-10- CM code: J09-J11
Influenza hospitalization	HV Claims	Inpatient encounter with ICD-10-CM code: J09- J11 listed as in any diagnosis position

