8.5. Study Size

Since the current study utilizes retrospective deidentified data without ability to recruit to a target, sample size calculations are not applicable. Further, this is a descriptive study without *a priori* specified hypotheses.

Initial data feasibility work has revealed approximately 19 million persons in the state of California with claims available in HealthVerity, among which approximately 25% are pediatric and 75% adult. Among these, approximately 12 million have at least one year of continuous medical and pharmacy enrollment. By end of 2023, we expect to have finished contracting to add approximately 565,000 additional persons. The proportion of these additional persons who will have 1-year continuous enrollment, and therefore the sample size estimates below have taken the conservative approach to not yet include these people.

We have identified 63% of persons in the claims data have at least one COVID-19 vaccine, and 16% received at least one bivalent dose. The claims population we have is not a random sample of Californians and may differ from the state's population in systematic ways (e.g. the age distribution). While differences may exist, we have high confidence in our ability to represent vaccination status for the individuals in our claims population.

We expect to begin to see XBB doses in data delivered in November 2023. Assuming uptake similar to that seen with the BA.4/5 vaccine, and non-differential uptake by age groups, we could anticipate in California:

(25% of 12 million are pediatric)*(16% uptake)*(60% of doses were Pfizer-BioNTech)

~ 288,000 pediatric XBB doses in California

(75% of 12 million are adult)*(16% uptake)*(60% of doses were Pfizer-BioNTech)

~ 864,000 adult XBB doses in California

Additional doses will be observed in Louisiana. In order to maintain patient de-identification, outcomes, covariates and subgroups will have at least 10 people in each category for inclusion in outputs. Throughout the protocol, this is referred to as "If sample size allows".

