Follow-up time: From date of FDA authorization/approval until the outcome of interest, or are censored at the first of the following: 6 months of follow-up, end of medical and/or pharmacy enrollment, receipt of a non-Pfizer BioNTech vaccine or receipt of a second BNT162b2 COVID-19 vaccine dose.

Primary outcome:

A COVID-19-related encounter, regardless of setting (primary outcome)

Secondary outcomes:

- An outpatient encounter with ICD-10-CM U07.1 "COVID-19" code
- An inpatient encounter with ICD-10-CM U07.1 "COVID-19" listed in any diagnosis position. As a sensitivity analysis, we will restrict to U07.1 in primary diagnosis field.

PFIZER CONFIDENTIAL

CT24-WI-GL02-RF02 5.0 Non-Interventional Study Protocol Template For Secondary Data Collection Study 01-Aug-2023

- An emergency department encounter with ICD-10-CM U07.1 "COVID-19" code
- COVID-19 critical illness, defined as intensive care unit [ICU] admission, mechanical ventilation, or inpatient death. If sample size allows, we will evaluate VE against each component separately in order to support V&E models.
- Non-COVID-19 respiratory infection: diagnosis of any of pneumonia, respiratory syncytial
 virus (RSV), rhinovirus and/or receipt of antibiotic prescription. If sample size allows, we
 will evaluate VE against each component separately in order to support V&E models.
- Negative control outcomes such as accidental injury, ingrown toenail or atopic dermatitis Exploratory outcomes:
 - An urgent care encounter with ICD-10-CM U07.1 "COVID-19" code
 - All-cause mortality within 3-months of COVID-19 encounter, regardless of setting
 - All-cause mortality within 3-months of COVID-19 outpatient encounter
 - All-cause mortality within 3-months of COVID-19 inpatient encounter
 - All-cause mortality within 3-months of COVID-19 emergency department encounter
 - All-cause mortality within 3-months of COVID-19 critical illness
 - All-cause mortality within 3-months of COVID-19 urgent care encounter

Measures of absolute and relative VE: For each outcome above, results will be calculated as:

- Absolute VE comparing vaccinated to unvaccinated persons, regardless of prior vaccination
- Relative VE will be calculated for each of the following mutually exclusive subgroups.
 - xBB.1.5 vaccinated vs xBB.1.5 unvaccinated persons who received BA.4/5 bivalent vaccine.

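### Aim 2: the 'non-COVID-19 respiratory infection' composite counts an antibiotic prescription on its own and has no rule for events also coded U07.1, so it is not specific to what it names

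*SAP*

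**What the plan says.** Three places define this pediatric secondary outcome, and they agree.

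- Aim 2 SAP, Section 5.3.2, Table 5.2: "Any encounter regardless of setting with ICD-10-CM code for diagnosis or NDC codes for antibiotics (codes in the Protocol Annex".
- Protocol Section 8.3, Table 4, labels the variable "Non-COVID-19 respiratory infections (pneumonia, RSV, rhinovirus, antibiotic prescriptions" and uses the same either/or rule.
- Protocol Section 8.7.2 lists diagnoses of pneumonia, RSV and "rhinovirus and/or receipt of antibiotic prescription".

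Both documents also plan component results, sample size permitting. In the protocol's words, "we will evaluate VE against each component separately in order to support V&E models". Protocol Section 8.5 sets that condition low: "outcomes, covariates and subgroups will have at least 10 people in each category for inclusion in outputs". The Aim 2 SAP, Section 5.7.2, adds a minimum number of events per model parameter.

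Two further rules bear on COVID-19 overlap. Section 5.2.2 of the Aim 2 SAP excludes "Persons with a diagnosis of COVID-19 in any setting ≤ 90 days prior to index (FDA EUA date per vaccine", which acts only before follow-up starts. Section 5.3.2 then says: "Each outcome will be assessed independently and experiencing one outcome will not be a censoring event for another outcome". It also keeps only the first instance of each outcome.

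**The concern.** The label makes two promises, that the event is respiratory and that it is not COVID-19. The stated rule secures neither for every event it counts.

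A drug code carries no indication, so a fill for a skin or urinary infection meets the definition. Because only the first instance counts, such a fill also becomes the child's composite event and hides a later pneumonia or RSV diagnosis from the composite.

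A pneumonia code or antibiotic claim that belongs to a COVID-19 episode also qualifies, because nothing removes it. One COVID-19 pneumonia episode can then be an event for the primary outcome and for the non-COVID-19 outcome.

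The outcome is named in the protocol's secondary objective (Section 7) and in the Aim 2 objective (SAP Section 4). Its VE could be read as evidence on protection against other respiratory infections. Dilution would hide a real effect, and COVID-19 overlap could create one. The same SAP table takes care over specificity for COVID-19 hospitalization, where it handles incidental codes, but sets no comparable condition here.

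**Working it through.** The plan gives no rate, VE or precision for this outcome, so there is no figure to reproduce. The check is a reading of the rules, followed by an illustration.

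**Reading the rules**

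1. Does an antibiotic claim need a respiratory diagnosis? All three definitions join the antibiotic arm with 'or' or 'and/or', and none adds a linking condition. No link is required.
2. Is a U07.1-coded event removed? The only COVID-19 exclusion looks back 90 days from index. During follow-up, outcomes are assessed independently and one does not censor another. It is not removed.
3. Which components are exposed? The antibiotic component is open to both faults and the pneumonia component to the second. RSV and rhinovirus are open to neither: no antibiotic rule applies to them, and a coded RSV infection is still RSV if U07.1 is also present.

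**Illustration**

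Treat components as rare and independent, so that the composite hazard ratio is roughly the mean of the component hazard ratios weighted by event share in unvaccinated time. Let c be the share of COVID-19-coded events and f the share of non-respiratory fills, on which the vaccine is assumed to have no effect. Then:

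composite VE = c × VE(COVID-19) + (1 − c − f) × VE(genuine non-COVID) + f × 0

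*Contamination.* Set VE against genuine non-COVID infection to zero. The composite VE is then c × VE(COVID-19). The Aim 2 SAP, Section 5.5, anticipates 20–40% for COVID-19. The shares c are assumed.

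| c (assumed) | VE 20% | VE 30% | VE 40% |
|---|---|---|---|
| 2% | 0.4 | 0.6 | 0.8 |
| 5% | 1.0 | 1.5 | 2.0 |
| 10% | 2.0 | 3.0 | 4.0 |

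Entries are spurious VE in percentage points. For example, 0.02 × 20 = 0.4 and 0.10 × 40 = 4.0.

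*Dilution.* With c = 0, the composite reports (1 − f) of any real effect. For assumed f of 30%, 50%, 70% and 90%, the surviving fraction is 0.7, 0.5, 0.3 and 0.1. The documents state no expected VE against non-COVID infection, so this cannot be turned into points without a further assumption.

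**Could a few points show up as an effect?**

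Table 5.4 of the Aim 2 SAP, at 3,000,000 children and VE 20%, gives 95% limits of 19 and 21 for 10,000 cases per 100,000, and 16 and 24 for 1,000 per 100,000.

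- SE(log HR) = [ln(1 − lower) − ln(1 − upper)] / (2 × 1.96)
- At 10,000: [ln 0.81 − ln 0.79] / 3.92 = 0.0250 / 3.92 = 0.0064. The smallest VE whose interval excludes zero is about 1 − exp(−1.96 × 0.0064) = 1.2%.
- At 1,000: [ln 0.84 − ln 0.76] / 3.92 = 0.1001 / 3.92 = 0.0255, which gives about 4.9%.

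The printed limits are whole numbers, so the first threshold is rough. True limits of 19.5 and 20.5 would give 0.6%, and 18.5 and 21.5 would give 1.9%. If the composite is as common as 10,000 per 100,000 (an assumption), a spurious effect of 1–4 points could exclude zero. At 1,000 per 100,000 it would not.

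**The case against.** **The code lists are out of view.** The Protocol Annex holds the antibiotic and diagnosis codes and was not among the documents reviewed. It may restrict the agents or the pneumonia codes, and for some exclusion criteria the SAP says that the Annex holds definitions as well as codes. This stands as a limit: it is not established that every antibiotic counts. But for this outcome the SAP points to the Annex for codes only. A drug list does not supply an indication, and a diagnosis list does not test whether U07.1 is also present.

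**Component results are planned.** This stands in part. The threshold of 10 people per category is low against 3,000,000 children, and the RSV and rhinovirus results answer a clean question. The antibiotic and pneumonia components keep the faults described, and so does the composite.

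**The label discloses antibiotic prescriptions, and Aim 2 covers resource use.** Broad antibiotic use is a legitimate outcome. That is a reason to report it under its own name, not inside a respiratory-infection composite.

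**The size rests on assumption.** This stands. No document gives the shares, and the 20–40% VE is for symptomatic COVID-19.

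A reader might go further and infer that the outcome captures neither respiratory nor non-COVID illness, or that component results are of no help. The documents do not support either inference. Pneumonia, RSV and rhinovirus are respiratory diagnoses, RSV and rhinovirus are pathogens other than SARS-CoV-2, and their separate results have neither fault.

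**Conclusion.** The definition as written lets an antibiotic prescription stand alone as a non-COVID-19 respiratory infection and states no exclusion for events that also carry U07.1. The composite and its antibiotic and pneumonia components are not specific to non-COVID-19 respiratory infection. This follows from the text and needs no numerical assumption, subject to the Annex adding no further condition.

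The size of the bias is unknown. With 2–10% of events COVID-19-coded (assumed), COVID-19 VE of 20–40%, and no true effect on other infections, the spurious VE is 0.4–4 points. Non-respiratory fills would dilute any real effect in proportion to their share. The two mechanisms act on the same composite, and under a true benefit they pull in opposite directions unless COVID-19 VE is no larger than VE against the other infections, so a reported value could not be interpreted without the event breakdown.

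This is one secondary outcome in a study described as having no hypotheses. The primary outcome does not depend on this definition. The change should be made, but the main VE result does not hang on it.

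**What to change.** In Table 5.2 of the Aim 2 SAP, and in the matching protocol text:

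1. Count an antibiotic fill in the composite only when it is linked to an encounter with a respiratory-infection diagnosis within a short window fixed before analysis.
2. Report all antibiotic use as a separate outcome under that name.
3. Do not count a pneumonia diagnosis, or a linked antibiotic fill, when the qualifying encounter or claim also carries U07.1. RSV and rhinovirus diagnoses can stay as they are.
4. Use any wider U07.1 window only as a sensitivity analysis. Such a window removes events according to COVID-19 status, which vaccination may affect. If the vaccine works, more genuine non-COVID events would be dropped from unvaccinated time, which biases VE downward. A same-encounter rule limits this.
5. Report event counts by component, and how many events were dropped under each rule, so that the actual shares replace the assumed ones.

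The cost is revised wording, a claims join and fewer events, with some loss of precision. No new data are needed.
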